1. INTRODUCTION

Endoscopic ultrasound (EUS) with fine-needle aspiration (EUS-FNA) has become an essential tool for the diagnosis of solid pancreatic lesions (SPLs) and extrapancreatic lesions with 85% sensitivity and 98% specificity [1].

Several factors have been studied to optimize outcomes of EUS-FNA [1], such as the use of rapid on-site evaluation (ROSE) for immediate cytopathologic assessment [2], needles calibres and types [3], number of needle passes [4], and sampling techniques [5]. Currently, sampling techniques include standard suction (SS), slow-pull (SP) and wet-suction (WS).

The SS was the first technique used during EUS-FNA. It is performed applying a negative pressure suction at the proximal end of the needle after the stylet is removed with an air-filled pre-vacuum 10/20 ml syringe [6].

Differently, in the SP technique, after advancing the needle inside the lesion, the stylet is slowly removed, thus applying a capillary suction, while the operator performs some needle back and forth movements inside the lesion [7].

The WS relies on pre-flushing the needle with saline to replace the column of air with fluid, followed by aspiration at the proximal end of the needle, using a pre-vacuum 10/20 ml syringe [8,9].

A recent meta-analysis including seven randomized controlled trials compared the outcomes of SS versus SP for sampling of SPLs with EUS-FNA has been published [10]. The SP technique demonstrated similar adequacy and accuracy when compared to SS, with a non-significant trend in favour of SP (OR = 0.82; 95 % CI 0.36–1.85; P = 0.63) and moderate heterogeneity that was not explained by the sensitivity analyses. However, a significant improvement in bloodiness of the samples using the SP has been demonstrated [10].

In a single-blinded randomized trial on 117 patients comparing the WS with the SS for FNA, the WS yielded in significantly higher cellularity (1.82 ± 0.76 vs. 1.45 ± 0.768 , $P < 0.0003$) and better specimen adequacy (85.5% vs. 75.2%, $P < 0.035$) [9]. Recently, Wang et al. compared diagnostic accuracy in SS and WS for FNA of solid lesions (intrabdominal and mediastinal) in a multicentre randomized controlled trial. Among the 269 patients with pancreatic ($n=161$) and non-pancreatic ($n=108$) lesions analysed, the WS had a significantly better histological diagnostic accuracy (84.9% [95% confidence interval (CI) 79.9%–89.0%] vs. 73.2% [95%CI 67.1%–78.7%]; $P = 0.001$), higher specimen adequacy (94.8% vs. 78.8%; $P < 0.001$), and less blood contamination ($P < 0.001$) than the SS technique [11].

All the aforementioned studies investigated the performance of the different sampling techniques in the setting of EUS-FNA. In the last decade, however, new EUS needles for the acquisition

of histological specimens have been developed with the purpose to overcome the limitations of cytology and obviate the need for ROSE.

In particular, end-cutting forward-acquiring needles (SharkCore™, Covidien/Medtronic, Boston, Massachusetts, and Acquire™, Boston Scientific, Marlborough, Massachusetts) have shown excellent histological yield [12,13], and several randomized trials have demonstrated their superiority compared with standard [14,15] and side-fenestrated needles [16], while they performed equally when compared each other in two randomized trials and one metanalysis [17-19]. Because of the high diagnostic accuracy of fine-needle biopsy (FNB) needles, current practice in moving from EUS-FNA to EUS-FNB [20].

The histological yield of newest generation histological needles is changing the role of EUS-FNB from diagnostic to prognostic and theranostic tool to drive precision medicine [21]. Development of next-generation sequencing (NGS) technologies has increased the speed and reduced the cost of sequencing the nucleic acids of cancer cells. The feasibility of NGS on EUS-FNB samples has been demonstrated [22] and requires a tumour fraction $\geq 20\%$ either for pancreatic duct adenocarcinoma (PDAC) [23] and pancreatic neuroendocrine tumors (pNETs) [24]. Therefore, EUS-FNB should guarantee a sample of adequate size and quality to perform molecular diagnostics.

Up to now, no studies investigating the impact of different suction techniques on histological yield and sample quality of specimens from solid lesions using EUS-FNB needles have been published.

2. STUDY AIMS AND ENDPOINTS

The primary aim of this study is to compare **the histologic yield** of EUS-FNB using the SP and the WS techniques. The primary endpoint is the rate of samples containing a tissue “core” (yes/no) for histological evaluation, defined as an intact piece of tissue of at least 550μ [i.e., specimens scored 3 using the tissue integrity score (see **Table 1**)]. The length of intact histological fragments will be measured by using dedicated software at each participating center.

Secondary aims include:

1) Sample quality in terms of tissue integrity and the blood contamination. A score will be applied according to **Table 1** and outcomes using the two technique will be compared.

Table 1 Sample quality scores (tissue integrity and blood contamination)

SCORE	TISSUE INTEGRITY
0	No cells/tissue
1	Cytological specimen (disaggregated cells representative of the target lesion not allowing for tissue architectural assessment)
2	Histologic microfragments (sample adequate for histological evaluation, namely an architecturally intact piece of tissue but without a “core”)
3	Histologic “core” (defined as an architecturally intact piece of tissue measuring at least 550 μ)
SCORE	BLOOD CONTAMINATION
0	Only blood
1	High blood contamination (>50% of the surface)
2	Moderate blood contamination (25-50% of the surface)
3	Low blood contamination (<25% of the surface)

2) Evaluation of tumor fraction with both techniques. The rate of samples collected with the two techniques containing an adequate tumor fraction $\geq 20\%$ (i.e., $\geq 20\%$ tumor cells in a background of benign nucleated cells) will be compared. Only PDAC and pNETs will be included for this aim.

3) Diagnostic accuracy using two sampling technique, measured against the final diagnosis. The final diagnosis will be assessed on surgical whenever available, and in non-resected patients will be based on the diagnostic work-up (combined outcomes of imaging studies and any additional biopsy sample result) and clinical course of the disease of at least 6 months. The Papanicolaou classification (**Table 2**, simplified) [25] will be used either for EUS-FNB samples and surgical pathology for pancreaticobiliary masses. Lymph nodes will be classified as benign or malignant. For the evaluation of submucosal lesions, GIST and neuroendocrine tumors will be considered as malignant. Immunohistochemistry investigations will be performed, if required for diagnosis, as in normal clinical practice.

Table 2 Diagnostic category and diagnoses according to the Papanicolaou classification

Diagnostic Category	Sampling Features
1	Not adequate
2	Benign/neoplastic benign 
 - chronic pancreatitis - autoimmune pancreatitis - intrapancreatic spleen - serous cystadenoma (solid type) - schwannoma
3	Atypical cells 
 - Scant population of atypical cells of unclear origin
4	Neoplastic other 
 - NET - solid pseudopapillary neoplasm - GIST
5	Suspicion for malignancy 
 - Atypical cells suspicious for adenocarcinoma
6	Malignant 
 - PDAC - neuroendocrine carcinoma - metastasis - other (specify)

3. PLAN OF INVESTIGATION

Design of the study

This is a multicenter, single-blind, randomized, controlled trial. All adult (≥ 18 years old) patients referred for EUS-FNB of solid lesions of the GI tract or adjacent to it will be assessed for eligibility. Patients with the following conditions will be included:

- Solid pancreatic lesions $\geq 1\text{cm}$
- Peri-GI tract lymph nodes $\geq 1\text{cm}$
- Peri-GI tract masses
- Lesions of the GI wall
- Signed informed consent

Patients with the following conditions will be excluded:

- Pancreatic cystic lesions (more than 50% of the volume)
- Diameter of lesion $\leq 1\text{ cm}$
- Lesion not seen at EUS
- Pregnancy
- Coagulopathy (platelet count $<50.000/\text{mm}^3$ and/or international normalized ratio >1.5);
- Severe cardiorespiratory dysfunction precluding endoscopy;
- Failure to provide informed consent

EUS-FNB procedures and samples processing

All the procedures will be performed by experienced endosonographers at each center and using a linear echoendoscope. A 22G end-cutting needle (SharkCore™ or Acquire™) will be used in all cases. The choice between the SharkCore and the Acquire needle will be left to the endosonographer's discretion or based on institutional disposition.

Four passes will be performed [27] using the same needle alternating the sampling techniques (SP and WS). The sequence of will be assessed in a randomized fashion.

For WS the stylet will be removed, and the needle will be pre-flushed with 1–2mL of saline. The lesion will then be punctured, and suction will be applied using a 10-mL pre-vacuum syringe [11]. The sample collected will be pushed into a formalin vial with saline.

For SP, after puncturing the lesion, the stylet will be slowly and gradually withdrawn for at least 40cm. The sample will be pushed into formalin using the stylet.

Each pass, regardless of the sampling procedure, the fanning technique [28] will be used. It consists of approximately 5-10 back-and-forth movements of the needle, positioned in different areas within the mass, by using the “up-down” dial of the echoendoscope and with minimal use of the elevator.. Afterwards, the needle will be withdrawn from the lesion.

The sample taken during 1st/3rd passes and 2nd/4th passes will be placed in two separate vials containing formalin and processed as standard histology. The flowchart in **Figure 1** illustrates the recruitment process. ROSE will be not used in any case.

Drop out

Patients will not be considered included in the study in the following situations:

- Impossibility to perform EUS-FNB (e.g., for the interposition of vessels or technical failures).
- Impossibility to complete the procedure according to the protocol (e.g., it was not possible to perform four needle passes).

Randomization and blinding

Once verified the eligibility to the trial, patients will be prospectively randomized in a 1:1 ratio in a cross-over design within each center into one of two study groups based on a computer-generated randomized blocks sequence (block size of 10) just before the procedure. Randomization will be stratified by type of lesion sampled (pancreatic versus other).

[figure not shown]
A data manager not involved in the data analysis or patient enrollment will generate the randomization lists and will prepare numerated sealed envelopes, containing the group assignment, that will be opened after study consent and EUS baseline assessment, just prior EUS-FNB. Patients will be randomly assigned into Group A and Group B in a 1:1 ratio. For Group A, the pass sequence is WS, SP, WS, SP. For Group B, the pass sequence is SP, WS, SP, WS.

The pathologist designated for the evaluation of the samples will be blinded on the type of TA technique performed and randomization during the entire study.

Follow-up

Patients will be followed for at least 6 months, in order to assess the outcome of surgical resection or clinical course of the disease.

Figure 1. CONSORT flow-chart of the study

Collected data and data management

The following data will be collected and included in a case record form (CRF) (see **CRF attached**):

- Sex
- Age
- Technical success (Y/N)
- Type of lesions (pancreatic/extrapancreatic/lymphnode)
- Lesion location
- EUS findings [site (e.g., head and size or the lesion), size (mm)]
- Needle type used (SharkCore 22G or Acquire 22G)
- Randomization (group A or B)
- Number of passes performed
- Fanning (Y/N)
- Histological findings (Tissue Integrity score, Blood Contamination score, tumor fraction >20% for pancreatic cancer and NET)
- Adverse events [29]
- Diagnostic category on EUS-FNB for pancreatic lesions
- Diagnosis for lymphnode (malignant/benign)
- Diagnosis on EUS-FNB for submucosal lesions (specify)
- Length (days) of the follow-up
- Patient/lesion's outcome at follow-up (death, weight loss/cachexia, surgery, lesion growth/infiltration/metastases appearance, lesion's stable or disappearance with patient well)
- Further sampling of the lesion (Y/N).
- Final Diagnosis (specify; e.g.; PDAC, NET, GIST, Leiomyoma, Malignant Lymphnode)

Enrollment and duration of study

Enrollment will be competitive between centers and will extend for a maximum period of 9 months after local Ethic Committee/IRB approval. It is plausible that Ethic Committee/IRB approval will be obtained at different time periods among the participating centers, thus requiring a total enrollment period of 18 months. A 6-month follow-up period is foreseen in order to evaluate the possible surgical treatment or other biopsy samplings or the evolution of the disease. We foresee a period of 3 months to complete the data analysis. The total duration of the study will be 27 months.

4. SAMPLE SIZE AND STATISTICAL ANALYSES

Sample size calculation

The sample size is calculated in the context of the primary binary outcome and considering the crossover design of the study with each lesion sampled with the two techniques. Assuming an expected pooled histological yield of 95% with WS [11] and 85% with SP [30,31] with $\alpha=0.05$, power=0.9 and calculating the proportion of discordant pairs (equal to 0.18) with the approximation of Machin, Campbell, Fayers, and Pinol (1997) due to the lack of the data in the current literature, the total required sample size should be of 185 patients. Assuming approximately 8% dropout rate, we calculated a final sample size of 200 patients.

Statistical analyses

The characteristics of the sample will be summarized by descriptive statistics (mean with standard deviation or median with interquartile range for continuous variables and frequency distributions for categorical variables).

For the analysis of the primary end-point, the percentage of cases in which a histological sample was obtained will be calculated in each study arm. In particular, it will be possible to evaluate, for each group, through the McNemar test, if there is a statistically significant difference between the histological capacity of the two sampling techniques.

Sample quality scores and rate of samples containing an adequate tumor fraction will be compared using the McNemar test. Furthermore, the accuracy of the two techniques will be estimated by calculating sensitivity, specificity, positive predictive value, negative predictive value, and Area Under the ROC Curve respect to the the final diagnosis.

All analyses will be performed using the SPSS software with a statistical level of significance of 5% and respective 95% confidence intervals. A two-tailed distribution will be used and statistically significance will be considered for $P<0.05$.

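### The primary McNemar test is written per group (pass sequence A or B), but the 185 patients are sized for one test on all pairs; read literally, each test has about 62% power by the plan's own formula, not 90%

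*Combined protocol and SAP*

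**What the plan says.** The primary aim in section 2 is to compare the histologic yield "of EUS-FNB using the SP and the WS techniques", with a yes/no core endpoint.

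Section 3 (Randomization and blinding) randomises patients 1:1 to two groups that differ only in pass order: "For Group A, the pass sequence is WS, SP, WS, SP. For Group B, the pass sequence is SP, WS, SP, WS". Section 3 (EUS-FNB procedures and samples processing) fixes the paired unit: "The sample taken during 1st/3rd passes and 2nd/4th passes will be placed in two separate vials". Each patient therefore contributes one WS vial and one SP vial.

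Section 4 (Sample size calculation) sizes the trial "considering the crossover design of the study with each lesion sampled with the two techniques" and concludes that "the total required sample size should be of 185 patients", raised to 200 for about 8% dropout.

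Section 4 (Statistical analyses) then says of the primary endpoint that "the percentage of cases in which a histological sample was obtained will be calculated in each study arm", and that "it will be possible to evaluate, for each group, through the McNemar test, if there is a statistically significant difference". For the secondary endpoints, the scores and the "rate of samples containing an adequate tumor fraction will be compared using the McNemar test", with no reference to groups.

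**The concern.** The sentence with the group qualifier is the only one that specifies the primary test. Group cannot sensibly mean technique there, because a McNemar test contrasts the two techniques within patients. The only other meaning in the visible text is sequence group A or B. The sentence then prescribes two tests, each on half the patients, while the sample size supports one test on all of them.

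Three things are at stake.

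- **No single primary conclusion.** The plan does not say whether one significant group is enough, whether both are needed, or what follows if they differ. The reading could be chosen after the data are seen.
- **Confounding within a group.** Group A always takes WS in passes 1 and 3 and SP in passes 2 and 4; Group B does the reverse. A test inside one group estimates technique plus pass order.
- **The reported percentage.** If study arm also means sequence group, the percentage mixes WS and SP samples and is a yield for neither technique.

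**Working it through.** **Inputs (section 4 unless noted).** WS 95%, SP 85%, so d = 0.10; discordant proportion pd = 0.18; two-sided alpha 0.05; power 0.90; 200 patients with about 8% dropout; 1:1 allocation (section 3). Evaluable patients: 200 × 0.92 = 184, so 92 per group if split equally.

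**Step 1: reproduce the plan's figure.**

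N = [z₀.₉₇₅·√pd + z₀.₉₀·√(pd − d²)]² / d²

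= [1.960 × √0.18 + 1.2816 × √0.17]² / 0.01

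= [0.8315 + 0.5284]² / 0.01 = 184.94, that is 185.

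This matches the stated number. The 185 is the requirement for one McNemar test on all pairs. The same power in each group would need 185 per group, 370 in total.

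**Step 2: power by the same formula.** Power = Φ{[d·√n − z₀.₉₇₅·√pd] / √(pd − d²)}.

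- n = 92: (0.9592 − 0.8315) / 0.4123 = 0.310, power 62.2%.
- n = 184: (1.3565 − 0.8315) / 0.4123 = 1.273, power 89.9%.

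**Step 3: power by enumeration.** The plan does not name a McNemar version, so three were enumerated over the discordant counts. The cell probabilities are (0.18 + 0.10)/2 = 0.14 favouring WS and (0.18 − 0.10)/2 = 0.04 favouring SP.

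| Version | One group, n = 92 | Pooled, n = 184 |
|---|---|---|
| Planning formula | 62.2% | 89.9% |
| Uncorrected | 64.4% | 91.9% |
| Exact | 55.4% | 88.2% |
| Continuity-corrected | 53.1% | 88.1% |

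If all 200 patients were analysed, n = 100 per group gives 65.9% by the formula and 57.6% to 68.7% enumerated.

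**Step 4: how often the two groups disagree.** With the same true effect in both groups and no order effect, the probability that exactly one is significant is 2p(1 − p):

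- uncorrected: 2 × 0.644 × 0.356 = 46%
- exact: 2 × 0.554 × 0.446 = 49%
- continuity-corrected: 2 × 0.531 × 0.469 = 50%

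**Step 5: error rate if either group counted.** The plan states no such rule; this shows only what it would cost. With no technique difference (both discordant cells 0.09) and n = 92, each test rejects 4.93% (uncorrected), 2.85% (exact) or 2.46% (continuity-corrected) of the time. 1 − (1 − p)² gives 9.6%, 5.6% and 4.9%.

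**Step 6: order effects, illustration only.** The documents give no order effect. Assume no technique difference, 90% average yield, independent vials within a patient and n = 92 per group.

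| Assumed yield, first / second vial | Discordant cells | One group rejects: uncorrected (exact) | Pooled rejects: uncorrected (exact) |
|---|---|---|---|
| 92% / 88% | 0.92 × 0.12 = 0.110; 0.88 × 0.08 = 0.070 | 14% (10%) | about 5% (3%) |
| 93% / 87% | 0.93 × 0.13 = 0.121; 0.87 × 0.07 = 0.061 | 27% (20%) | about 5% (3%) |

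The pooled figures were simulated. Pooling protects because the order effect has opposite signs in the two groups.

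**The case against.** The strongest reply is that section 4, read as a whole, points to one pooled test. The sample size is a total for a paired comparison, the aim in section 2 sets technique against technique, and the secondary McNemar sentence has no group qualifier. The primary sentence is permissive in tone and sits in a protocol with other rough phrasing, so this may be loose drafting and not a plan for two primary tests. On that view the power loss belongs to a reading that nobody intended, and the either-group and order-effect figures rest on a rule and on effects that the plan does not contain.

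Much of this is fair. A pooled test probably was intended, and every power figure above is conditional on the literal reading. The ends of the 53% to 64% range come from different test versions, so each should be compared with its own pooled counterpart in the table. The either-group error is materially inflated only for the uncorrected test. The alternating passes may limit any order effect. Pooling balances order only approximately, since blocks of 10 within centre and lesion type may stay incomplete and patients without four passes are dropped after randomisation.

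None of this supplies the missing sentence. A confirmatory analysis has to be fixed by the text. Here the text that fixes it says something different from the sample-size paragraph, and an analyst who followed it would get the weaker and confounded result.

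**Conclusion.** The concern holds: the primary-analysis sentence is wrong as written and must be corrected before data are analysed. It prescribes a test per sequence group, whereas the trial is sized for one test on all pairs.

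Followed literally, it costs between 27 and 35 percentage points of power, comparing like with like: 62% against 90% by the plan's formula, 64% against 92% uncorrected, 55% against 88% exact, and 53% against 88% continuity-corrected. It also leaves nearly an even chance of two results that disagree, with no rule to resolve them.

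These figures assume the plan's own rates and discordance, 184 evaluable patients split equally, and the same effect in both groups. The confounding of technique with pass order inside a group follows from the design and needs no assumption; only its size is unknown. Confidence is high on the inconsistency. The authors' intention is an inference, and it favours the pooled test.

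**What to change.** Replace the two sentences on the primary endpoint with: *The primary analysis is a single two-sided 5% McNemar test of WS versus SP on all evaluable pairs from Groups A and B combined. Core rates are reported by technique, with the paired difference and its 95% confidence interval.*

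In addition:

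- State which version of the McNemar test applies (uncorrected, exact or continuity-corrected).
- Label any results by sequence group as descriptive.
- Optionally, prespecify an order-adjusted paired analysis as a sensitivity analysis, such as the Mainland-Gart test or conditional logistic regression with technique and order. It is not needed as the primary test, because combining the 1:1 sequences largely balances order.

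The cost is wording only. Sequence group is already on the CRF, and the design, data collection and sample size are unchanged.

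### The McNemar test is named for two ordered 0–3 quality scores with no cut-point or multi-category extension; a paired ordinal test should be named instead

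*Combined protocol and SAP*

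**What the plan says.** Section 2 sets the first secondary aim as "Sample quality in terms of tissue integrity and the blood contamination" and continues: "A score will be applied according to Table 1 and outcomes using the two technique will be compared". Table 1 gives each score four ordered levels. Integrity runs from 0 (nothing obtained) to 3, a core, "defined as an architecturally intact piece of tissue measuring at least 550" µm. Blood contamination runs from 0 (blood only) to 3, "Low blood contamination (<25% of the surface").

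The data list in section 3 records the scores themselves: "Histological findings (Tissue Integrity score, Blood Contamination score, tumor fraction >20% for pancreatic cancer and NET").

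Section 4 names one test for these outcomes: "Sample quality scores and rate of samples containing an adequate tumor fraction will be compared using the McNemar test".

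The only cut-point for either score appears in the definition of the primary endpoint in section 2: "specimens scored 3 using the tissue integrity score". Blood contamination has no cut-point anywhere.

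**The concern.** Each patient supplies one vial per technique, so each score yields a paired four-by-four table. McNemar works on a paired two-by-two table. To apply it, someone must either collapse the score at a cut-point or move to a multi-category extension, and the plan does neither.

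Two things are at stake:

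- **An open choice.** For each score the analyst could use the Bowker symmetry test or any of three cuts (1 or more, 2 or more, 3). That is four options per score and 4 × 4 = 16 combinations for the aim, with nothing to fix the choice before the scores are seen.
- **Lost information.** Bowker ignores the ordering that Table 1 builds in, and a dichotomy discards part of it.

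Blood contamination deserves a settled analysis: the Introduction cites it as an outcome on which suction techniques have differed.

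**Working it through.** **1. The plan's own figure.** The documents give no calculation for the scores, only for the primary endpoint. With discordant proportion 0.18, difference 0.95 − 0.85 = 0.10, two-sided 5% and 90% power:

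n = [1.960 × √0.18 + 1.2816 × √(0.18 − 0.10²)]² / 0.10² = (0.8315 + 0.5284)² / 0.01 = 184.94, so 185.

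This matches section 4. The point below concerns a different comparison and leaves that number alone. For the scores I take 200 × (1 − 0.08) = 184 pairs.

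**2. What the sentence could mean.**

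| Reading | Tissue integrity | Blood contamination |
|---|---|---|
| Bowker symmetry test | Valid; ignores order; P value has no direction | Same |
| Cut at 3 | Repeats the primary endpoint | Not stated |
| Cut at 2 or more | A different question (adequate for histology); not stated | Not stated |
| Cut at 1 or more | Not stated | Not stated |

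As written, the analysis cannot be run for blood contamination. For integrity, the only stated cut would produce the primary result again.

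**3. Cost of leaving the cut open.** Simulation with no true difference, counting runs in which at least one of the three cuts gives P < 0.05:

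- Uncorrected McNemar: 12–14%.
- Exact McNemar, under another assumed distribution: 9–10%.
- One Wilcoxon signed-rank test: about 5%.

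The ceiling for three tests at 5% is 3 × 5% = 15%, so these values are plausible. Each single test keeps its own error rate; the excess arises only if the cut is picked after seeing the data.

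**4. Power of each reading.** The documents give no score distribution, shift or within-patient correlation, so all three are assumed. Scores come from a correlated latent normal cut into four levels: 184 pairs, correlation 0.3, 4,000 runs per scenario. McNemar is the uncorrected version. Percentages in the first column are for scores 0/1/2/3. The shift in the last row is the one that takes 85% to 95%: z(0.95) − z(0.85) = 1.645 − 1.036, about 0.608 SD.

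| Assumed scenario | Wilcoxon | McNemar at 3 | Bowker |
|---|---|---|---|
| Blood 5/20/35/40%, shift 0.3 SD | 83% | 73% | 55% |
| Blood 5/15/20/60%, shift 0.3 SD | 74% | 69% | 43% |
| Blood 10/30/35/25%, shift 0.3 SD | 87% | 67% | 58% |
| Integrity 3/4/8/85%, shift 0.4 SD | 67% | 69% | 27–41% |
| Integrity 3/4/8/85%, shift 0.608 SD | 92% | 94% | 59–77% |

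The Bowker ranges reflect 6 degrees of freedom or only the non-empty cell pairs. In the first blood scenario the sign test had 80% and McNemar at 2 or more had 60%. In the first integrity scenario these were 68% and 45%.

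For blood contamination, Wilcoxon exceeds McNemar at 3 by 83 − 73 = 10, 74 − 69 = 5 and 87 − 67 = 20 points. It exceeds Bowker by 28, 31 and 29 points. For integrity, a cut at 3 loses nothing (69% against 67%; 94% against 92%), while Bowker loses a good deal.

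**5. Sensitivity to correlation.** First blood scenario:

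- At 0.5: Wilcoxon 92%, McNemar at 3 80%, Bowker 65–68%.
- At 0.7: Wilcoxon 98%, Bowker 81–87%.

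The Bowker gap narrows to 98 − 87 = 11 to 98 − 81 = 17 points, and the order of the two tests does not change.

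**The case against.** The strongest reply is that this is under-specification, not a wrong test. Stating one cut per score in advance and keeping McNemar would be valid, so insisting on an ordinal test is a preference based on power. For integrity the power argument fails outright, since a cut at 3 does as well as Wilcoxon. For blood contamination it rests on invented distributions, and both techniques sample the same lesion with the same needle, so a high correlation, where the Bowker gap shrinks, is plausible. Wilcoxon also treats the steps of Table 1 as comparable in size, which is doubtful for none, cytology, microfragments and core. Finally, only one secondary aim is touched, and the raw scores will be on file, so any repair stays possible.

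Much of this is fair. A pre-stated cut is a valid repair, the equal-step assumption is a real limit, and the power figures are illustrations. Three points remain. The plan states no cut for this comparison, so the defence describes a plan that has not been written. For integrity, the one cut available leaves the secondary comparison with no content of its own. And that the raw scores will be on file is why the choice should be fixed before they are analysed.

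**Conclusion.** The concern holds. The named test does not fit the two scores as Table 1 defines them, and nothing in the documents closes the gap. That conclusion follows from the text and does not depend on any simulation.

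The size is moderate and confined to secondary aim 1. Choosing the best cut afterwards would raise the false-positive rate from about 5% to 9–14%. For blood contamination, a cut at 3 costs roughly 5–20 points of power against Wilcoxon, and Bowker about 30 points at correlation 0.3 and 11–17 at 0.7. For integrity, the case against a cut at 3 is redundancy with the primary endpoint, not power. These figures rest on assumed score distributions, shifts and correlations. The primary analysis, the sample size of 185 (200 with dropout) and the tumour-fraction comparison stand. This should be corrected before the scores are analysed.

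**What to change.** Replace the part of the section 4 sentence that deals with the scores by wording such as:

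*The 0–3 tissue-integrity and blood-contamination scores will be compared within patient by the two-sided Wilcoxon signed-rank test. The percentages of patients scoring better with WS, better with SP, and equal will be reported, with the difference between the first two percentages and its 95% confidence interval for paired proportions.*

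If the team does not accept the steps of Table 1 as comparable in size, it should name the paired sign test instead, or a cumulative-logit GEE with technique and vial order that reports a common odds ratio with its 95% confidence interval. Only one of these should be named as the main test, and that should be settled before the scores are analysed.

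Keep McNemar for the binary outcomes (core yes/no, tumour fraction at least 20%) and for any further dichotomy whose cut is stated in advance, for example integrity 2 or more. If the team prefers to keep McNemar alone, it must state one cut per score, using a cut other than 3 for integrity, and accept the loss of information.

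The cost is a sentence or two in section 4. The data and the software stay the same, and neither the primary analysis nor the sample size changes.
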